Echocardiography has been increasing used in understanding the cardiac structure and risk of stroke among patients with AF, with left atrial size, left ventricular wall thickness, and left ventricular dysfunction recognized as independent predictors of AF [7]. Increasing evidence supports that the left atrial strain measurements can be a predictor of outcomes among AF patients, including stroke and AF recurrence after catheter ablation [8], [9]. We aim to further explore left atrial strain measurements, including left atrial global longitudinal strain (LA GLS), as predictors of maintenance of normal sinus rhythm post-cardioversion. We anticipate to find that a lower LA GLS will predict AF recurrence. To do this, we will study patients with AF at Pen Bay Medical Center who have undergone cardioversion, measuring their LA GLS pre-cardioversion, and assess maintenance of sinus rhythm 6 months post-cardioversion. We anticipate that our study will confirm LA GLS as a marker for maintenance of sinus rhythm post-cardioversion.

Hypothesis

A lower left atrial global longitudinal strain is a predictor of atrial fibrillation recurrence post- electrical cardioversion.

Specific Aims

Include patients from the MaineHealth system into a retrospective study to explore the relationship between left atrial global longitudinal strain (LA GLS) and AF. Patient data will derive from existing EPIC data for MaineHealth patients from January 1, 2017 to June 30, 2021. The EPIC data extract will include: diagnosis of atrial fibrillation, documented echocardiogram, and electrical cardioversion during the study time period. For patients who meet the study criteria outlined in Section 3 below, we will collect demographic and clinical data from EPIC manually (see Section 5 below). The primary outcome measure to be collected includes maintenance of sinus rhythm at least six months post-cardioversion.

Include patients from Pen Bay Medical Center (PBMC) into the same study, however in a prospective portion of the study. These patients will be consented and followed prospectively until six months after cardioversion.

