2. We will assess LA GLS using an automated measurement tool called AutoSTRAIN by TOMTEC-ARENA (<https://www.tomtec.de/products/application-finder/autostain/>). The historic echocardiograms from patients who meet the study inclusion criteria will be uploaded into this software, which was newly acquired by the PBMC Cardiology Department. MaineHealth Information Services are currently working with study staff to assure appropriate security compliance within the network. LA GLS has not been routinely collected previously from echocardiograms performed at PBMC because of a lack of such technology.
3. We will use statistical methods to describe the relationship between LA GLS and maintenance of sinus rhythm six months post-cardioversion among the AF patients included in this study.

2 Study Design

This study has both retrospective and prospective components. There is an enrollment goal of 500 subjects.

For the retrospective portion, patients will be identified for inclusion in the study based on a previous documented diagnosis of AF, have a documented echocardiogram done prior to the cardioversion with images available in the MaineHealth electronic medical record (EMR), and have undergone electrical cardioversion at a MaineHealth institution.

For the prospective portion of the study, patients will be identified by the PBMC echocardiographic technicians prior to elective cardioversion. The patient will be consented prior to the administration of any sedative. If the patient consents, they will be followed for 6 months after the procedure via the EMR only. The prospective portion of the study will only be conducted at PBMC and not at other MaineHealth institutions due to the lack of staffing capacity at the investigative site.

3 Subject Selection and Withdrawal (if applicable)

3.1 *Inclusion Criteria*

- Patients identified at any MaineHealth site with a documented diagnosis of AF (at any point in time prior to the cardioversion) and who have undergone any cardioversion.
- The patient would also need to have had an echocardiogram within six months pre-cardioversion (performed for any reason) with a well visualized atrial roof in order to perform the measurements accurately using the TOMTEC-ARENA software.
- For the prospective portion of the study – must be willing to provide informed consent

3.2 *Exclusion Criteria*

- Patients with a mitral regurgitation greater than moderate (effective regurgitant orifice $\geq .2 \text{ mm}^2$)

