- Patients who have undergone surgical valve repair or replacement, if the procedure was done with a thoracotomy
- Echocardiographic images not of sufficient quality to obtain the study measurements as determined by the investigator

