3.3 Subject Recruitment and Screening

Subjects will be identified using a retrospective chart review within EPIC, between January 1, 2017, through June 30, 2021. These patients will have a diagnosis of atrial fibrillation, a documented echocardiogram, and cardioversion therapy. The study staff will review the medical records in EPIC of these patients and screen for the other inclusion/exclusion elements described above.

For the prospective portion of the study, potential subjects will be identified by the PBMC echocardiographic technicians prior to cardioversion. Either one of the echocardiographic technicians or one of the PBMC Clinical Research coordinators will explain the study to the patient and obtain informed consent.

4 Storage of Study Materials

Study data will be entered into and maintained in a web-based, HIPAA-compliant REDCap database which has a password protected login and only accessed by appointed study staff. These staff include a cardiac sonographer, the clinical research manager at PBMC, and the Rural Research Navigator at the Center for Outcomes Research and Evaluation (CORE), each of which will have full read/write access to the database. Information about study subjects will be kept confidential and managed according to the requirements of the Health Insurance Portability and Accountability Act of 1996 (HIPAA). Once the dataset is complete, all identifiers (medical record numbers and dates of health events or services) will be deleted and subjects will be identified by a unique study ID#, assigned by REDCap. Only de-identified data will be downloaded for analysis.

5 Data collection and management

The study staff- one cardiac sonographer, the clinical research manager at PBMC, and the Rural Research Navigator at CORE- will request an extract of EPIC patient data from Enterprise Reporting based on the inclusion criteria of atrial fibrillation, a documented echocardiogram, and electrical cardioversion therapy, including these codes:

	ICD-9	ICD-10	CPT
Atrial fibrillation	427.31		
Atrial flutter	427.32		
Paroxysmal atrial fibrillation		I48.0	
Persistent atrial fibrillation		I48.1	
Chronic atrial fibrillation		I48.2	
Typical atrial flutter		I48.3	
Atypical atrial flutter		I48.4	
Unspecified atrial fibrillation		I48.91	
Unspecified atrial flutter		I48.92	
Transthoracic stress echo, complete			93350
Transthoracic stress echo, complete w cont EKG			93351
Transthoracic echo cardiac anomalies			93303

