 - b. Determine maintenance of sinus rhythm at least six months post cardioversion
 - c. Medical Record Number
 - a. Sex
 - b. Age
 - c. Race/ethnicity
 - d. Weight
 - e. Date of first atrial fibrillation diagnosis
 - f. Number of AF recurrence visits
 - g. Antiarrhythmic medications
 - h. Smoking status
 - i. Number of shocks at cardioversion
 - j. Post-ablation procedure
 - k. Hypertension
 - l. Diabetes
 - m. COPD
 - n. Obstructive sleep apnea
 - o. Renal impairment
 - p. Hyperthyroidism
 - q. Coronary artery disease
 - r. Congestive heart failure
 - s. Left systolic dysfunction
 - t. Left diastolic dysfunction
 - u. Left ventricular hypertrophy
 - v. Valvular heart disease
4. Also within this population, obtain echocardiographic features/ measurements:
 - a. GLS of LA of 4 chamber
 - b. GLS of LA of 2 chamber

c. LAVI (Left atrial volume index)

Aside from the echocardiographic features, all of the above data elements will be in EPIC and extracted into a REDCap database. The echocardiographic features will be obtained by the two cardiac sonographers utilizing the TOMTEC software, and will document these in REDCap. Patient medical record numbers and dates of health events or services (date of cardioversion, date of atrial fibrillation diagnosis, and date of echocardiogram) will be removed from the database after the six month follow-up visit and documentation of normal sinus rhythm occurs. Time lapsed between echocardiogram(s) and duration of atrial fibrillation will be calculated fields created in REDCap based on dates of echocardiogram(s) and date of first atrial fibrillation diagnosis, respectively. Once the time lapsed variables have been created, the date variables will be removed from the database.

Subject information will be kept in the PBMC Echocardiographic lab and the PBMC Clinical Research office, which are both locked when unattended. Information entered into a REDCap database which is password protected. Information about study subjects will be kept confidential and managed according to the requirements of the Health Insurance Portability and Accountability Act of 1996 (HIPAA).

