- Protected health information (PHI), which will be collected from subject charts in this study, include demographics (age, sex), echocardiogram results, and maintenance of normal sinus rhythm. Patient medical record numbers will be used for linking the prospective information related to maintenance of normal sinus rhythm, and will be deleted after this information is documented in REDCap.
- Time lapsed between echocardiogram(s) and duration of atrial fibrillation will be calculated fields created in REDCap based on dates of echocardiogram(s) and date of first atrial fibrillation diagnosis, respectively. Once the time lapsed variables have been created, the date variables will be removed from the database.
- Only the cardiac sonographers and the PBMC clinical research nurse manager will have access to this information.

6 Analysis Plan

The duration of AF will be calculated for each patient utilizing the date of first AF diagnosis and the date(s) of cardioversion(s). Descriptive statistics will be used to summarize the demographic and clinical characteristics of patients included in the study, with continuous variables presented as a mean + standard deviation and categorical variables as frequencies/percentages of the total.

A t-test will be utilized to compare the mean LA GLS among patients documented to have maintenance of sinus rhythm at 6 months to those who have not.

A binary logistic regression model will be developed in order to model any predictive factors (independent variable: echocardiographic features/measurements) among those who have maintained sinus rhythm vs. those who have not (dependent variable: sinus rhythm yes/no) within six months of cardioversion. Criteria for selecting other variables listed above for entry into the logistic regression model will be based on univariate analysis of each variable. Variables determined to have a significant univariate test with a p-value cutoff of 0.05 will be included in the model. Variables deemed not significant will be assessed for confounding by observing parameter estimate changes >10% when variables are excluded from the full model. Analyses will be performed using SAS by the Rural Research Navigator at the Center for Outcomes Research and Evaluation at the Maine Medical Center Research Institute.

7 Confidentiality

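### In the retrospective part, the sonographers who measure left atrial strain may see the rhythm outcome, and nothing masks the reading, the choice of echocardiogram or image rejection.

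*Combined protocol and SAP*

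**What the plan says.** **Who measures.** Section 5: "The echocardiographic features will be obtained by the two cardiac sonographers utilizing the TOMTEC software", with the results entered in REDCap. LAVI is among these features.

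**Who sees the outcome.** Section 4 lists a cardiac sonographer, the clinical research manager and the Rural Research Navigator, "each of which will have full read/write access to the database". Sections 5 and 7 list maintenance of sinus rhythm among the information collected and then state: "Only the cardiac sonographers and the PBMC clinical research nurse manager will have access to this information". Section 5 also counts one sonographer among the study staff who review EPIC charts for eligibility. The rhythm outcome is drawn from the same record system.

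**When.** Section 5 lists the rhythm outcome (item 3b) ahead of the echocardiographic measurements (item 4). It expects that some patients will already have had their follow-up visit when the study starts.

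**What is left to judgement.** Section 3.1 requires a clear view of the atrial roof and accepts an echocardiogram done for any reason in the six months before cardioversion. Section 5 allows for more than one echocardiogram per patient and gives no rule for choosing. Section 3.2 excludes "Echocardiographic images not of sufficient quality to obtain the study measurements as determined by the investigator".

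**What is automated.** The Specific Aims (item 2) name AutoSTRAIN as an automated tool for LA GLS.

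No section provides for masked reading, coded images, or a quality decision locked before the outcome is known. Section 4 removes identifiers only when the dataset is complete, which is too late to mask a reader.

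**The concern.** LA GLS is the exposure in both planned analyses. Section 6 says: "A t-test will be utilized to compare the mean LA GLS among patients documented to have maintenance of sinus rhythm at 6 months" with those who did not maintain it, and the logistic model takes the echocardiographic measurements as predictors. The staff also know which result is expected. Section 1 says: "We anticipate to find that a lower LA GLS will predict AF recurrence".

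If a reader knows who relapsed, that knowledge can affect three steps: which echocardiogram is used, whether the image is accepted, and any manual part of the measurement. Neither the t-test nor covariate adjustment can separate such an effect from a real association. A positive result would then be open to the objection that it reflects reader expectation, and the study would have no data with which to answer.

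**Working it through.** **1. The plan's own figure.** Section 2 says: "There is an enrollment goal of 500 subjects". No SD, effect size, event rate or power accompanies it, so it cannot be reproduced. It serves here only as the total N.

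**2. Inputs.**
- N = 500 (Section 2). Section 8 warns that this may not be reached, so N = 250 is shown as well.
- Two-sided alpha of 0.05 for the t-test: assumed. The plan gives 0.05 only for variable selection ("Variables determined to have a significant univariate test with a p-value cutoff of 0.05 will be included in the model").
- Outcome split: not given. Assumed 250/250 and 150/350 for N = 500, and 75/175 for N = 250.
- Differential reading shift b, in SD units: not given. Assumed 0.05 to 0.15.
- True difference: zero, so every rejection is a false positive.

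**3. Formula.** With se = sqrt(1/n1 + 1/n0), the false-positive rate is Φ(b/se − 1.96) + Φ(−b/se − 1.96).

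Example at 250/250 with b = 0.10: se = sqrt(2/250) = 0.0894 and b/se = 1.118. The rate is Φ(−0.842) + Φ(−3.078) = 0.200 + 0.001 = 20.1%.

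| Split | se | b = 0 | 0.05 SD | 0.10 SD | 0.15 SD |
|---|---|---|---|---|---|
| 250/250 | 0.0894 | 5.0% | 8.6% | 20.1% | 38.9% |
| 150/350 | 0.0976 | 5.0% | 8.1% | 17.6% | 33.6% |
| 75/175 | 0.1380 | 5.0% | 6.5% | 11.2% | 19.2% |

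For scale, the smallest observed difference that reaches significance is 1.96 × se: 0.175, 0.191 and 0.271 SD respectively.

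**4. Dilution by prospective patients.** Here b is the average shift over everyone analysed. If only a fraction f of each outcome group is read with the outcome known, the average is f × b. With f = 0.5 (assumed; the plan gives no split between the two parts), a 0.10 SD shift becomes 0.05 SD, and the rate at 250/250 falls from 20.1% to 8.6%.

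**5. Selective rejection.** Suppose 5% of the recurrence images are rejected, about 12 of 250. If these were exactly the highest-strain images, the mean would shift by φ(1.645)/0.95 = 0.103/0.95 = 0.109 SD. With se = sqrt(1/238 + 1/250) = 0.0906, the false-positive rate is about 22%. If the rejection judgement has correlation r with strain, the shift is r × 0.109: 0.033 SD and 6.5% at r = 0.3, and 0.054 SD and 9% at r = 0.5. The 22% is therefore a ceiling that requires r = 1.

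**The case against.** The strongest reply is that the strain value comes from software, and that the plan screens images before it measures them. The Specific Aims and Section 5 both describe uploading images from patients who already meet the criteria. LA GLS was not routinely collected at the PBMC site before. Whoever rejects an image would then usually have no strain value, and rejection could follow strain only loosely. This stands as far as it goes: it weakens the rejection route and limits the reading route. It does not remove them. The software does not choose among several echocardiograms or decide whether the atrial roof is seen well enough, and the plan does not rule out rejection after upload.

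A reader might also infer four stronger things that the documents do not support.

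- *The investigator who judges image quality sees the outcome.* The investigator is on neither access list. The documents do not say what the investigator sees. The firmer route is the sonographer among the staff who review charts and screen eligibility.
- *The results are biased towards the hypothesis.* Access permits bias. It does not show that bias occurs, or in which direction.
- *The whole study is affected.* For prospective patients the outcome does not exist until six months after cardioversion. Whether their images are read before then is not stated.
- *The damage could not be repaired.* A masked re-read of archived images, including rejected ones, could correct both routes. It would depend on images still being linkable to study IDs, and Sections 4 and 5 plan to delete record numbers.

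**Conclusion.** The point holds for the retrospective part. The plan's own text gives the strain readers access to the rhythm outcome, which often exists before they read, and nothing masks the reading, the choice of echocardiogram or the quality judgements. Both main analyses can be biased as a result.

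The size cannot be estimated from the documents. On the stated assumptions, a shift of 0.05 to 0.15 SD gives a false-positive rate of 8.6% to 39% at 250/250, 8% to 34% at 150/350, and 6.5% to 19% at 75/175. The lower end is close to nominal, and any share of masked or prospective reads reduces the figures further. They show that a modest shift would matter at this sample size; they do not predict that one will occur. The change is worth making because it is cheap and prevents an objection that is hard to answer afterwards.

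**What to change.** Amend Sections 4 and 5 as follows.

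1. The clinical research manager or the Rural Research Navigator does the EPIC eligibility review and outcome abstraction, and passes pre-cardioversion images to the sonographers under study ID only. Hiding REDCap forms alone is not enough, because a sonographer who reviews charts can see the outcome in EPIC.
2. The echocardiogram is chosen by a fixed rule, for example the last eligible one before cardioversion. Image quality is judged against a short written criterion. The quality decision, LA GLS and LAVI are completed and locked in REDCap before outcome fields are opened to the readers or the quality judge.
3. REDCap user rights hide the outcome and recurrence forms from the readers and the quality judge. The same setting should hide strain from the person abstracting the outcome, since a dictated note can leave room for interpretation.
4. Every quality rejection is logged with its reason and tabulated by outcome. Section 5 describes REDCap entry only for patients who meet the criteria, so no such log exists at present.
5. The access lists are reconciled: the Navigator appears in Section 4 but not in Sections 5 and 7, and Section 4 has one sonographer where Section 5 has two.
6. Images from prospective patients are read and locked before the six-month outcome is known.

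If reading has already begun, item 4 and a masked re-read of a sample, including rejected images, remain useful while images can still be linked.

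The cost is some reallocation of chart review and scheduling among staff already named. It needs no extra reader and no change to the enrolment goal.

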Transthoracic echo cardiac anomalies, limited			93304
Transthoracic echo complete w color & spectral			93306
Transthoracic echo complete wo color & spectral			93307
Transthoracic echo limited			93308
Cardioversion (nonemergency), elective, electrical			92960

The study staff will review the medical records in EPIC of these patients and screen for the other inclusion/exclusion elements described above. Patients who meet this criteria will be included in the study and have their medical record number documented in REDCap (a secure, HIPAA compliant, web-based database portal). If these patients are living and scheduled for a follow-up visit at PBMC, they will be consented to be included in the study by one of the study staff. If they do not consent to be included in the study, their information will be deleted from the REDCap database. If they are no longer living or have already had a follow-up visit at the time of the study start date, consent will not be obtained. For those included in the study, medical record numbers, along with demographics, BMI, date of atrial fibrillation diagnosis, antiarrhythmic medications, date(s) of echocardiogram(s) and cardioversion(s) performed, and whether sinus rhythm was maintained at least six months post-cardioversion either by electrocardiogram (ECG), holter monitor, telemetry monitoring or cardiologist dictated note. These patients' echocardiography images will be obtained pre-cardioversion from EPIC and uploaded to the TOMTEC software in order to obtain the LA GLS measurements (as continuous data).

GLS is derived via validated methods [10] using a calculation of:
$$\epsilon = \frac{L1 - L0}{L0} \times 100\%$$

It has proven to be clinically reproducible as reported in a prior study [11]. While the TOMTEC vendor does not provide normal range values for clinical interpretation, the literature provides GLS measurement data for comparison among nine different software vendors, including TOMTEC [12].

In short, we will:

1. Identify patients at with AF, who obtained an echocardiogram and cardioversion.
2. Consent patients who meet the inclusion criteria who are living and who will be returning for their six month follow-up visit.
3. For patients who have consented or who are deceased, or who have already presented for their six month follow-up visit by the time the study has started, the following information will be collected:
 - a. Dates of echocardiogram(s) and cardioversion(s) performed

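### The hypothesis is about AF recurrence, but rhythm at the end of the cardioversion is not collected, so patients who never converted cannot be reliably told apart from those who relapsed

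*Combined protocol and SAP*

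**What the plan says.** The Hypothesis reads "A lower left atrial global longitudinal strain is a predictor of atrial fibrillation recurrence post- electrical cardioversion", and the Background repeats the expectation: "We anticipate to find that a lower LA GLS will predict AF recurrence".

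The outcome is worded differently. Under Specific Aims, "The primary outcome measure to be collected includes maintenance of sinus rhythm at least six months post-cardioversion"; the third aim is to describe the "relationship between LA GLS and maintenance of sinus rhythm six months post-cardioversion among the AF patients included in this study".

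Section 3.1 admits patients "with a documented diagnosis of AF (at any point in time prior to the cardioversion) and who have undergone any cardioversion". Nothing in Sections 3.1 or 3.2 requires that the procedure succeeded or removes those in whom it failed.

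The only rhythm result listed in Section 5 is "whether sinus rhythm was maintained at least six months post-cardioversion". The same list has a count of shocks, "Number of AF recurrence visits" (not defined), and the dates of cardioversions. It has no item for rhythm when the procedure ended.

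Section 6 uses a t-test to "compare the mean LA GLS among patients documented to have maintenance of sinus rhythm at 6 months to those who have not", and a logistic model whose dependent variable is sinus rhythm, yes or no. Neither has a separate category for a failed cardioversion.

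**The concern.** A patient cannot relapse from a rhythm that was never restored. The not-maintained group can contain two kinds of patient: those who converted and later relapsed, and those who never converted. The Background itself treats initial success and long-term maintenance as separate matters.

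If failures have lower strain than relapses, the pooled comparison overstates the link between strain and recurrence. If they have higher strain, it dilutes that link and could reverse its sign. If their mean strain is the same, the mean difference is unbiased however many failures there are. With no field for conversion, a reader of the results cannot tell which case applies.

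The gap also becomes permanent. Sections 4 and 5 have record numbers and event dates deleted once data are complete, after which a missing rhythm result cannot be linked back to the chart.

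**Working it through.** The plan gives no effect size, SD or power for the LA GLS comparison, so there is no figure of its own to reproduce. The check asks how far pooling could move the answer.

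**Inputs from the protocol**
- Enrollment goal: 500 (Section 2).
- Initial success: 68-98% (Background). The title of the cited source concerns acute AF, whereas the extract in Section 5 uses an elective procedure code, so applying this range to the cohort is an assumption.

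**Assumed inputs, not in the protocol**
- Half of converted patients maintain sinus rhythm (varied below).
- A true maintained-versus-relapsed strain difference of 0.30 SD, or zero.
- Failures and relapses differ in strain by 0, 0.3 or 0.5 SD.
- A two-sided 5% t-test, with power from the noncentral t distribution.

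**Number of failures.** 500 × (1 − 0.98) = 10; 500 × (1 − 0.68) = 160.

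**Share of failures in the not-maintained group.** With failure rate f, maintained = relapsed = 250(1 − f), and the not-maintained group is 250(1 − f) + 500f. The share is s = 500f / [250(1 − f) + 500f].

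**Bias.** The pooled difference equals the true recurrence difference plus s × gap, where the gap is how much lower strain is in failures than in relapses.

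| Failure rate | Failures | Not maintained | s | Bias, gap 0.3 SD | Bias, no gap |
|---|---|---|---|---|---|
| 2% | 10 | 255 | 0.039 | 0.012 SD | 0 |
| 10% | 50 | 275 | 0.182 | 0.055 SD | 0 |
| 20% | 100 | 300 | 0.333 | 0.100 SD | 0 |
| 32% | 160 | 330 | 0.485 | 0.145 SD | 0 |

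A gap in the other direction gives the same sizes with the opposite sign.

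**Three assumed cases**
- (a) Failures have the same strain as relapses; true difference 0.30 SD.
- (b) Strain is unrelated to failure, so failures sit at the mean of converted patients; true recurrence difference 0.30 SD. The pooled difference is 0.30(1 − s) + 0.15s = 0.294, 0.273, 0.250 and 0.227 SD at the four rates.
- (c) Strain is unrelated to recurrence but lower in failures by 0.3 or 0.5 SD. The pooled difference is 0.3s or 0.5s.

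| Failure rate | (a) pooled / converted only | (b) pooled / converted only | (c) pooled test significant, 0.3 SD | (c) pooled test significant, 0.5 SD |
|---|---|---|---|---|
| 2% | 92% / 91% | 91% / 91% | 5% | 6% |
| 10% | 91% / 89% | 86% / 89% | 9% | 17% |
| 20% | 91% / 85% | 78% / 85% | 19% | 45% |
| 32% | 89% / 79% | 67% / 79% | 34% | 73% |

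In (a) restriction to converted patients only loses power. In (b) pooling loses power at failure rates of 10% and above. In (c) a significant result would be read as support for a recurrence link that does not exist.

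**Simulation check.** Allowing for the wider SD of the mixed group (20,000 runs per cell), case (c) with a 0.5 SD gap gives 5.4%, 16.6%, 43.1% and 71.6%, close to the formula.

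**Sensitivity to the maintenance rate.** At 32% failure, with 30% to 60% of converted patients maintaining, case (c) ranges over 19-43% (0.3 SD) and 44-84% (0.5 SD).

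**The case against.** The strongest reply is that the planned analysis is right for the outcome the study names. The primary outcome, the third aim, the t-test and the logistic model all concern sinus rhythm at six months. The Background's motive is to identify good candidates before the procedure, and for that question a failed conversion is properly a bad result. On this view only the word recurrence is out of place, and rewording the hypothesis would close the gap without new data. This stands as a defense of the pooled analysis, which should be kept. It does not let that analysis support a recurrence claim.

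Second, no rule says how a failed procedure is coded. To speak of maintaining a rhythm presupposes that it was restored, so an abstractor might leave such patients out. That is fair: the Section 6 wording makes a code of no the likelier reading, but the handling is unspecified. If failures were dropped informally, the database would not show that either.

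Third, other items might identify failures. Several shocks can end in success, a relapse may first be found at six months, and a closely spaced repeat cardioversion may mean failure or early relapse. These are weak proxies.

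Fourth, every strain gap above is assumed, and the largest percentages combine the worst end of a range drawn from another setting with a 0.5 SD gap. At 2% failure the effect is negligible. This stands, and it limits the claim.

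Finally, conversion occurs after the echocardiogram, so a converted-only analysis conditions on a later event and may carry selection of its own. That is a reason to report both analyses. It does not remove the need for the second, because recurrence is defined only among converted patients.

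**Conclusion.** The concern holds. Confidence is high that rhythm at the end of the procedure is missing from the listed data and that the analysis as written does not separate failures from relapses. The consequence in this cohort is unknown. Pooling misstates the recurrence association only if failures are not rare and their strain differs from that of relapses, and no figure in the protocol settles either point. Under the stated assumptions the bias runs from nothing to about 0.15 SD for a 0.3 SD gap, in either direction. The study is not invalid, and its analysis of sinus rhythm at six months is sound in this respect. The change is worth making because it is cheap, the hypothesis needs it, and it cannot be made after identifiers are deleted.

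**What to change.** Add one REDCap field, abstracted from the chart before record numbers and dates are removed: whether the patient was in sinus rhythm at the end of the cardioversion that starts the six-month follow-up (yes/no). Because Section 5 allows more than one cardioversion per patient, state which one that is.

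In Section 6:
- State that patients who did not convert count as not maintained in the all-patients t-test and logistic model, and keep both as the analysis of the stated outcome.
- Report the number of failed conversions and their LA GLS.
- Repeat both analyses in converted patients, and rest any statement about recurrence on that repeat, noting that it conditions on conversion.

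The cost is one more item from a chart already under review, a short rule for the index procedure, and a few sentences in Section 6. The repeat is smaller: 340 to 490 of 500 patients at 68-98% success. It can have less power, for example 79% against 89% at 32% failure when failures and relapses have the same strain, in a study that already doubts it will reach 500. The all-patients analysis loses nothing.
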